6.2. Study Day 1 Visit

This visit may or may not occur on the same day as the screening visit.

Pre-Treatment

- If Study Day 1 does not occur on the same day as screening and there has been active vaginal bleeding since screening, the transvaginal ultrasound must be repeated.
- The subject will be questioned to obtain baseline information about her demographic characteristics and her medical, coital, menstrual, pregnancy, and contraceptive history. She will be given the following questionnaires to complete at home prior to inserting misoprostol and return at her next visit: CES-D and the Perceived Stress Scale.
- Rh-immune globulin 50 µg (“MICRhoGAM”) will be administered within 72 hours of this visit if the subject is Rh-negative and has not recently received Rh-immune globulin.
- Additional blood will be drawn (20 cc) and it will be stored for analysis of proteins and hormones.
- Vital signs, weight, and height (to calculate BMI) will be measured.
- A pelvic examination and/or Gonorrhea and Chlamydia testing may be performed if indicated
- The subject will be randomly assigned to one of the two study groups: 800µg (vaginally) misoprostol (group 1) or misoprostol 800 µg (vaginally) preceded by 200 mg mifepristone po (group 2). See Method for Assigning Subjects to Treatment Groups Section 3.1

Treatment

- If the participant is randomized to group 2, she will be given 200mg of mifepristone. She will swallow the tablet prior to being discharged from the study visit.

- All subjects will be given four 200 µg misoprostol tablets to place vaginally approximately 24 hours later at home.
- The subject will be offered prescriptions for pain relievers per local standards at each site.
- The participant will be instructed to abstain from sexual intercourse until the passage of the pregnancy has been confirmed.
- The subject will receive instructions about what to expect after misoprostol administration as per standard of care.
- A diary will be distributed to collect information about bleeding, pain medication use, and symptoms. The subject will be instructed on how to properly complete the diary. The subject should bring this diary to each visit.
- A follow-up appointment will be made for Day 3.

Treatment may be delayed per subject preference. If treatment is delayed, and there has been active vaginal bleeding since the last transvaginal ultrasound, the ultrasound must be repeated prior to dispensing drug.

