6.4 Study Day 8 Visit (or Phone Call)

This visit will occur between study day 6-12. For those who were confirmed to have passed the pregnancy or had an aspiration procedure on Study Day 3, this visit will instead be a phone call to evaluate for bleeding or possible need for further evaluation.

- If this visit occurs in person, vital signs will be measured.

- Subjects who are scheduled to return for a visit on study day 8 will have a transvaginal ultrasound examination performed by a masked ultrasonographer. A pelvic exam will be performed if indicated.
- If no gestational sac is seen, the subject will receive contraception counseling and plan for a follow-up phone call on study day 30.
- If the examination demonstrates a persistent gestational sac, the options will be given for an aspiration procedure, a second dose of misoprostol or expectant management. The expectant management plan will include weekly visits for evaluation until the miscarriage is complete. These weekly visits will include a review of symptoms and adverse events, and an exam or ultrasound as indicated. They will also be offered active management if appropriate.
- Completed diary will be reviewed with subject. Adverse events will be reviewed and recorded.
- If subject requires additional visits, a new diary will be distributed.

6.5 30 Day Phone Call

All subjects will be contacted by telephone 30 days (range 25-36) after study day 1. Information on additional symptoms and treatment during the extended period will be recorded. Subjects will be asked to report any additional adverse events. The Post-Study Acceptability Questionnaire will be completed at this time, which will include the following scales: CES-D, Perceived Stress Scale, Adverse Child Experiences Questionnaire (ACE), and the Social Support Interview. The primary outcome of success (tissue expulsion after 1 dose of misoprostol with no additional need for medical/surgical intervention) or failure is ultimately confirmed at this 30-day point.

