7.2. Statistical Methods

Primary Analysis: Baseline demographic characteristics of the subjects in the two groups will be examined. If the randomization is executed correctly, we expect no significant difference between the two groups on these variables. If there is an imbalance on certain variables (mostly likely by chance) and these variables also affect the outcomes variables, we will control for these variables using indirect standardization, Mantel-Haenzel stratified analysis or multivariable logistic (for categorical outcome) or linear regression (for continuous outcome). If there is a gross imbalance between the two groups, we will conduct in-depth evaluation to identify factors that may adversely affect randomization. Multivariable logistic and linear regressions will be used to adjust for the imbalance.

We will explore outcomes by clinical site; if there is no significant overall difference among the sites (homogeneous), we will pool sites together. However, if there is significant overall difference, we will identify which site(s) differ from others. Pairwise comparison will be conducted with Scheffe adjustment of significance level. In all following analyses, site will then be an independent variable for adjustment.

Both intent to treat and compliant populations will be analyzed. For categorical data, chi-square test will be used. For continuous variables, t-test will be used if the distribution is normal; otherwise rank-sum test or log transformation will be used. The following outcomes will be evaluated:

- Success rates between study arms for early pregnancy failure;
- Frequency of side effects and serious adverse events between study arms;
- Patient's satisfaction, anxiety, and acceptability of the treatment regimens;
- Cost analysis to compare these two treatments.

The outcome is defined as gestational sac expulsion with one treatment dose on Study Day 3 and no need for surgical intervention or medical intervention within 30 days of treatment. The overall success proportion, along with 95% confidence intervals, will be calculated for each treatment group. The

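### Section 7.2 specifies no analysis for the CES-D and Perceived Stress scores beyond a generic unadjusted test, and the early score is taken too late to serve as a clean baseline

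*Combined protocol and SAP*

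**What the plan says.** Section 6.2 (Study Day 1 Visit) hands each woman "questionnaires to complete at home prior to inserting misoprostol and return at her next visit: CES-D and the Perceived Stress Scale". It lists this among the pre-treatment steps, ahead of randomization, but the forms go home with her. At the same visit she is randomized, and a woman in group 2 takes mifepristone: "She will swallow the tablet prior to being discharged from the study visit". Misoprostol follows at home about 24 hours later in both groups. Sections 6.3 and 6.4 mask the ultrasonographer; no masking of participants is described, and group 1 takes no tablet at the visit.

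The 30-day call (section 6.5) includes a questionnaire "which will include the following scales: CES-D, Perceived Stress Scale", so the same two instruments are repeated.

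On analysis, section 7.2 gives one rule for continuous variables: "For continuous variables, t-test will be used if the distribution is normal; otherwise rank-sum test or log transformation will be used". Adjustment is conditional: "If there is an imbalance on certain variables (mostly likely by chance) and these variables also affect the outcomes variables, we will control for these". Linear regression is the tool offered for a continuous outcome when that condition is met. The passage opens with baseline demographic characteristics, so it is unclear whether a psychological score would come under it. The outcome list in section 7.2 covers satisfaction, anxiety and acceptability, and section 3.3 lists quality of life; neither section names CES-D or the Perceived Stress Scale.

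**The concern.** When a scale is measured before treatment and again at follow-up, the usual efficient analysis regresses the follow-up score on arm and the earlier score. That removes the between-woman variation which the earlier score predicts, and it corrects for chance differences in starting distress without a decision made after seeing the data. Nothing of this kind is planned here. If the generic rule applies, the early scores play no part unless someone judges the arms imbalanced. A normality check would also decide whether the result is a mean difference, a rank comparison or a log-scale contrast, so the effect measure is not fixed in advance.

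The trial is sized on success rates alone, so power for these scales depends on how well they are analysed. A change to the SAP alone would not be enough, however: a score recorded after allocation is known, and in one arm after a study drug, may already carry part of the treatment effect.

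**Working it through.** **The plan's own figure.** The documents give no SD, effect size or correlation for either scale. The only sample-size figure is for the primary endpoint (section 7.1: 85% v 70%, 134 per group). With two-sided α = 0.05 and 80% power (neither sidedness nor power is stated for this calculation; both are inferred from the match), n = [1.960·√(2 × 0.775 × 0.225) + 0.842·√(0.70 × 0.30 + 0.85 × 0.15)]² / 0.15² gives 121 per group. The continuity correction raises this to 134, as stated. This point leaves that figure unchanged.

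**Inputs for the Day 30 scores.** 150 women per arm less the 5% loss allowed in section 7.1 is 142.5, taken as 142. Two-sided α = 0.05 and 80% power are assumed. The correlation r between early and Day 30 scores is assumed to lie between 0.1 and 0.7.

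**Unadjusted comparison.** Smallest detectable difference = (1.960 + 0.842) × √(2/142) = 0.3325 SD.

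**Adjusted for a pre-randomization score.** The standard error is multiplied by √(1 − r²), and the equivalent unadjusted sample is 142/(1 − r²).

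| Assumed r | SE factor | Fall in SE | Detectable difference (SD) | Equivalent unadjusted women per arm | Power at 0.333 SD |
|---|---|---|---|---|---|
| none (unadjusted) | 1 | – | 0.3325 | 142 | 80% |
| 0.1 | 0.995 | 0.5% | 0.331 | 143 | 80% |
| 0.3 | 0.954 | 5% | 0.317 | 156 | 84% |
| 0.5 | 0.866 | 13% | 0.288 | 189 | 90% |
| 0.7 | 0.714 | 29% | 0.237 | 278 | 98% |

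**Adjusted for the early score as now scheduled.** Suppose that knowing the allocation, or taking mifepristone, has already moved the early score by s SD between arms. The regression then estimates the total effect minus r × s. With s assumed to be 0.1 to 0.2:

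- r = 0.3: the estimate moves by 0.03 to 0.06 SD
- r = 0.5: by 0.05 to 0.10 SD
- r = 0.7: by 0.07 to 0.14 SD

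The fall in detectable difference at the same correlations is 0.3325 − 0.317 = 0.015, 0.3325 − 0.288 = 0.045 and 0.3325 − 0.237 = 0.095 SD. These are different quantities, but they are of the same order, and a larger sample would not shrink the distortion. The timing therefore has to be settled before the adjustment can be recommended as the main analysis.

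**The case against.** The strongest reply is that an unadjusted comparison of randomized arms is valid, that these scales are not named endpoints, and that the plan does provide for linear regression when an imbalanced variable affects the outcome. All of this stands. It limits the point to efficiency and prespecification on secondary outcomes. The conditional route is still a weak substitute: it is decided after the data are seen, gives no planned precision gain when the arms look balanced, and may not reach these scores.

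A reader might go further and infer that the plan has chosen a t-test or rank-sum test for the Day 30 depression and stress scores, and so discards precision already paid for that new SAP wording alone would recover. The documents do not support this. The rule is generic and neither scale is named, so what can be shown is that their analysis is unspecified. Nor does the current schedule yield a score from before randomization, so there is no clean baseline to discard, and the remedy needs a small change to the Day 1 procedures.

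The size of the gain is also open to challenge. The early form is self-completed at home and the Day 30 scales are obtained by telephone, which could lower the correlation, and forms not returned would reduce the gain further.

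**Conclusion.** The point holds as a modest improvement to secondary outcomes. Two scales are measured twice, no analysis of them is specified, and the default that would apply ignores the earlier score. As scheduled, that score follows allocation in both arms and mifepristone in group 2, so adjusting for it could bias the comparison. With a pre-randomization score, the standard error would fall by about 5% to 29% for r between 0.3 and 0.7, and by almost nothing at r = 0.1. These correlations are assumptions, as is the 0.1 to 0.2 SD shift used to illustrate the bias. The documents give no evidence that such a shift occurs; they show only that the schedule leaves room for one.

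**What to change.** 1. Have both questionnaires completed at the Day 1 visit before randomization, instead of at home afterwards.
2. Name the Day 30 CES-D and Perceived Stress scores as secondary outcomes in section 7.2. Prespecify, for each, a linear regression on arm, site (the stratification factor in section 5.3) and the woman's pre-randomization score on that scale. Report the adjusted mean difference with a robust or bootstrap confidence interval, so that no normality check selects the effect measure.
3. If the timing cannot change, keep the comparison unadjusted for the early score as the main analysis, show the adjusted one as a sensitivity analysis, and state that the early score was recorded after allocation and, in group 2, after mifepristone.

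The cost is a few minutes of added visit time, a small edit to section 6.2 and a paragraph in section 7.2. No new instrument is needed.

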Our hypotheses state that (1) biomarkers of endometrial decidualization and trophoblast function in the maternal circulation prior to treatment will predict the success of medical management and that (2) quantitative evaluation of a single biomarker or combination of biomarkers, combined with clinical characteristics, will accurately predict the women who will benefit from medical management overall and will identify those women who may especially benefit from combination treatment.

3 Study Design

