7.1. Sample Size Determination

Sample size calculations are based on detecting differences in the success rates between the misoprostol only and combined groups. Based upon prior research, we would expect a 60-71% single-dose success rate in the misoprostol only group [25]. Our preliminary data showed a 90% single-dose

success rate in the combined group using the proposed study regimen [11]. If we assume a conservative 85% success rate estimate for combined (C) and 70% success in the misoprostol only (M), we require 134 participants/group to show a difference if one is there (Table 2). To arrive at the total number of women needed to enroll, we inflate this estimate by 10% for loss to follow-up (5%) and interim analysis (5%). We will have adequate power to show a difference in success rates for all proportions above 10%. Thus, our proposed recruitment goal of 300 women (150/group) will enable us to find a clinically meaningful difference of 15% and confidently find the expected difference (20%) between groups.

Combination success rate	Misoprostol only success rate				
	50%	60%	65%	70%	75%
80%	n = 45 C: ±11.7% M: ±14.6%	n = 91 C: ±8.2% M: ±10.1%	n=151 C: ±6.4% M: ±7.6%	n = 313 C: ±4.4% M: ±5.1%	n = 1134 C: ±2.2% M: ±1.7%
85%	n = 33 C: ±12.2% M: ±17.1%	n = 57 C: ±9.3% M: ±12.7%	n=83 C: ±7.7% M: ±10.3%	n = 134 C: ±6.8% M: ±7.8%	n = 270 C: ±4.2% M: ±5.1%
90%	n = 25 C: ±11.8% M: ±19.6%	n = 38 C: ±9.5% M: ±15.6%	n=51 C: ±8.2% M: 13.1%	n = 72 C: ±6.9% M: ±10.6%	n = 113 C: ±5.5% M: ±8.0%
95%	n = 18 C: ±10.3% M: ±23.8%	n = 26 C: ±8.4% M: ±19.2%	n = 31 C: ±7.7% M: ±17.0%	n = 42 C: ±6.5% M: ±14.0%	n = 55 C: ±5.8% M: ±11.5%

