Once all participant phlebotomy specimens have been obtained, we will be able to derive a predictive model for successful medical management vs. failure for all subjects. Separate predictive models will then be built for each treatment arm, and any differences found here will lay foundations for future research. Accurate assessment of gestational age (GA) can be a challenge in women who present with EPF, and GA may in fact be a confounder in the relationship between hormone levels and the nature of the demise. Depending on time of presentation relative to time of demise, biomarker levels may be more a reflection of the actual GA, or may in fact be impacted by duration of demise (i.e. β hCG, P_4 may start declining after demise occurs). We can utilize last menstrual period dating (LMP) with the caveat that LMP is not always certain. To overcome this measurement error problem, we will also analyze a

subset of women with a sure LMP and for whom ultrasound dating is consistent with LMP. If the model for this subset is consistent with the model for the full data, or GA is not found to significantly modify the relationship, only the full data model will be presented.

Biomarker levels will be summarized overall, and by treatment group, using standard descriptive statistics. We will use graphical methods, such as lowess smoothers, to determine the shape (linear or non-linear, potential cut-points for classifying levels) of the relationship between the biomarker level and probability of success, and subsequently for inclusion as predictors in a multivariable logistic model. We will analyze a subset of women with a sure LMP and for whom ultrasound dating is consistent with LMP separately for the most accurate analysis of the relationship between biomarker concentration and the characterization of an EPF that will respond well to medical management. We can compare this definitive LMP group to the group of women in whom LMP is unsure. We will calculate the sensitivity, specificity, and positive and negative predictive values for each biomarker. The predictive accuracy of different cutoffs will be evaluated using ROC curves.

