Logistic regression and classification and regression trees (CART) will be used to develop a predictive model for successful management of early pregnancy failure, which will serve as the basis for a clinical predictive index [66-68]. Our group has used this methodology with success [69,70]. Initially the predictive model will only include biomarkers, and then both biomarkers and epidemiologic and clinical characteristics will be considered in the predictive model. The sensitivity of the predictive index (i.e., proportion of patients with success who are defined as “high chance of success” by the rule) will be of primary interest [71]. The negative predictive value will also be calculated using the derived sensitivity and specificity with the population prevalence of success. This value is also of clinical interest.

For model building, we will enter all biomarkers that will have shown in the bivariate analysis at least borderline associations with the endpoints of interest ($p < 0.20$), as well as interaction terms that are suggested by the results of the explanatory model. Terms will then be removed from the model using a backward elimination procedure, removing factors which cause an insignificant change in the sensitivity of the model. To test the change in sensitivity between models (with and without the variables), we will use McNemar’s test. In particular, we will be comparing the proportion of correctly classified cases of success between models. The rule would involve calculating a score for each person, based on the actual values of the regression coefficients. The goal is to utilize all variables that improve the sensitivity of the model. Unlike the explanatory model, whose goal is to determine which variables are associated with success, the predictive models will be developed in order to determine which combination of variables best predicts the outcome. Additionally, variables and interactions included in the model must be biologically plausible.

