To be useful, a clinical rule must be easily applied. In order to ensure easy understanding and unhindered application, the variables and parameters comprising the predictive score will be simplified with two methods: 1) by recalculating the predictive score using values of the coefficients, rounded to the nearest integer, and 2) by calculating the score simply as the sum of the dichotomous independent variables identified by the model. (It will be necessary, for this approach to recode continuous predictors as dichotomous variables.) This will result in the most parsimonious model. The performance of the new rules will then be compared with that of more complete models using ROC curves. We plan to evaluate potential cutoffs of each marker to optimize our ability to distinguish among successes and failures.

We will also approach our predictive modeling using CART. Candidates that have an individual area under the curve (AUC) > 0.6 will be considered. CART is useful in identifying complex relationships between biomarkers and clinical outcomes. These analyses recursively split observations into two

groups (nodes), t_L and t_R , based on the covariate that maximizes a given split function. In the case of a continuous outcome, a commonly used split function is the reduction in sums of squares error, i.e. the amount of variability explained by the split. The best split is defined to be the one that best predicts the response where the best predictor is defined to be the one that maximizes the split function. All splits of the observations in each of the resulting nodes are then considered and the best split identified. This process is repeated recursively until a stopping rule is achieved (e.g. no further splits exist with greater than 5 observations in each of the resulting nodes). We will employ 10-fold cross-validation to assess the significance of the resulting tree as described in Breiman [72]. The sensitivity and specificity of the CART versus logistic model will be compared using ROC curves, to determine the best predictive rule for management success. CART software will be used to evaluate combinations of biomarkers creating a tree maximizing sensitivity and a tree maximizing specificity. Data will be combined into a three-tiered algorithm to maximize accuracy.

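### The plan asks which women especially benefit from combination treatment but names no treatment-by-marker contrast; differences between separately built arm models do not answer that for null to moderate markers

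*Combined protocol and SAP*

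**What the plan says.** Section 2 gives two hypotheses under the secondary objective. The second holds that one or more biomarkers, taken with clinical characteristics, will predict who does well on medical management overall and "will identify those women who may especially benefit from combination treatment".

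Section 7.2 first derives one predictive model for all subjects. It continues: "Separate predictive models will then be built for each treatment arm", and "any differences found here will lay foundations for future research". It does not say how the two arm models are to be compared.

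For the logistic models, markers enter on a bivariate p<0.20. So do "interaction terms that are suggested by the results of the explanatory model", provided they are biologically plausible. Backward elimination follows, "removing factors which cause an insignificant change in the sensitivity of the model", judged by McNemar's test. For CART the screen is: "Candidates that have an individual area under the curve (AUC) > 0.6 will be considered". The bootstrap at the end of section 7.2 validates the accuracy of the prediction rule.

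**The concern.** Whether some women especially benefit is a question about how the difference between arms changes with the marker. Two models built separately each describe prognosis within one arm. If their marker lists differ, the reason may be differential benefit, chance, or unequal information: at the design rates the misoprostol arm has about twice as many failures as the combination arm. A threshold rule applied arm by arm cannot tell these apart. Retention by change in sensitivity does not help, because it measures classification and not a difference between arms.

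At stake is an explicit secondary hypothesis. Without a stated contrast, the trial could end with two unlike marker lists and no estimate of how far the arms differ. Later studies of individualized treatment might then be built on chance differences.

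**Working it through.** **Inputs from the documents.** Success 70% on misoprostol alone and 85% on the combination, 134 per group required, 150 per group recruited (section 7.1); 1:1 allocation (section 5.3); entry at p<0.20 and the AUC screen of 0.6 (section 7.2); overall alpha 0.05 (section 7.4).

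**Assumptions.** The documents give no marker effect sizes, so a range of odds ratios (OR) per SD is used. The marker is standard normal, one marker is fitted at a time, and the entry rules are applied within each arm. AUC is counted in either direction.

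**The plan's own figure.** For 70% against 85%, two-sided alpha 0.05 and 80% power (power and sidedness are assumed), the two-proportion formula gives 121 per group, or 134 with continuity correction. The stated 134 is reproduced and is not in question. The plan gives no figure for the arm models.

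**Expected failures.** 150 × 0.30 = 45 on misoprostol alone; 150 × 0.15 = 22.5 on the combination. With 5% loss (about 142 per arm): 42.6 and 21.3.

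**Null marker, by hand.** The arms are independent, so P(enters one model only) = p1(1 − p2) + p2(1 − p1). With p1 = p2 = 0.20 this is 2 × 0.20 × 0.80 = 32%.

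**Same OR in both arms.** 10,000 simulated trials per row, 150 per arm:

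| OR per SD | enters at p<0.20: misoprostol / combination | one arm only, p<0.20 | one arm only, AUC>0.6 | interaction test, p<0.05 |
|---|---|---|---|---|
| 1.0 | 20% / 19% | 32% | 17% | 5.0% |
| 1.25 | 49% / 39% | 50% | 39% | 5.2% |
| 1.5 | 83% / 68% | 38% | 49% | 4.8% |
| 1.75 | 96% / 86% | 18% | 31% | 5.1% |
| 2.0 | 99% / 94% | 7% | 13% | 4.9% |
| 2.5 | 100% / 99% | 1% | 2% | 4.7% |

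Check at OR 1.5: 0.832 × 0.321 + 0.679 × 0.168 = 0.267 + 0.114 = 38%. Further runs gave 50% at OR 1.3, 38% to 40% at 1.5 and 14% at 1.8. At 142 per arm every figure is within 3 points.

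The entry columns show the unequal information: at OR 1.5 the same marker is picked up in 83% of trials in one arm and 68% in the other. The interaction test compares the two log odds ratios directly and stays near its nominal 5%.

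**Precision of the contrast.** At 150 per arm and OR 1.5, the standard error of the difference in log OR is about 0.31. The 95% CI for the ratio of odds ratios is therefore the estimate multiplied or divided by exp(1.96 × 0.31) = 1.84. Power at 142 per arm is 26% for OR 1.0 against 1.5, 60% for 1.0 against 2.0 and 81% for 1.0 against 2.5.

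**Scale.** An equal OR is not equal absolute gain. With OR 1.8 in both arms, intercepts of 0.912 and 1.851 give 70% and 85% success overall, and ln 1.8 × 1.5 = 0.882. At −1.5 SD, predicted success is 50.8% and 72.5%, a gain of about 22 points. At +1.5 SD it is 85.7% and 93.9%, a gain of about 8 points.

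**The case against.** Four points on the other side carry weight.

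- A reader might infer that the plan will present chance differences as proof of who benefits. Section 7.2 does not say so: "any differences found here will lay foundations for future research" gives them hypothesis-generating status. This lowers the severity. The mismatch remains, because section 2 states the differential claim as a hypothesis of this trial.
- A reader might infer that separate models can never answer the question. They can: the difference between the two arms' coefficients for a marker, with its standard error, is the interaction estimate. What is missing is the stated contrast. A formal comparison is unspecified, not excluded.
- A reader might infer that treatment interactions are ruled out. They are not. The explanatory regression includes treatment group, so a treatment-by-marker term could be suggested by the data and pass the plausibility requirement. It would still be data-driven, and kept or dropped on sensitivity.
- A woman's absolute gain can vary with a marker whose OR is the same in both arms, as the scale calculation shows. Arm-specific predicted risks speak to that, and an interaction coefficient alone does not. This stands, and the fix below covers both scales.

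The contrast will also have low power for modest effects. That argues for reporting intervals and an exploratory label, not for leaving the contrast out.

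**Conclusion.** The concern holds in a limited form. The plan states a differential-benefit hypothesis and names no contrast that addresses it. For markers from no effect up to a moderate one, differing marker lists between arms are not evidence of differential benefit: a marker acting identically in both arms enters only one model in roughly a third to a half of trials for OR 1.0 to 1.5 per SD under the p<0.20 rule. The problem fades as markers strengthen, to 14% at OR 1.8 and 1% at 2.5, so it should not be described as general.

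These sizes rest on the design success rates, 142 to 150 women per arm and the assumptions listed with the calculation. They concern the entry step only; the later elimination on sensitivity was not simulated. The primary comparison and the sample size are unaffected.

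**What to change.** For the differential-benefit hypothesis, add to section 7.2:

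- a prespecified list of markers;
- for each, one pooled logistic model with treatment, the marker as a continuous variable, treatment × marker, and site;
- the interaction estimate with its 95% CI, under a stated multiplicity rule across the list;
- the predicted absolute difference in success between arms, across the range of marker values;
- a statement that these results are exploratory, with the per-arm models kept as descriptive output.

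The cost is SAP wording and a few more model fits, with no added participants, visits or blood samples. The drawback is imprecision: power is about 26% for OR 1.0 against 1.5 per SD, so an interval that includes no interaction must not be read as showing equal benefit.
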